### 9.4. Blinding

This is a non-interventional study and is blinded only with respect to the data analysts. The care workers need access to participant names and demographic data to support their visits. To enable participant collected data to be correlated with hospital and GP records collected during the study period, it will be necessary to use identifiable data. This is explained in clear language in the Participant Information Sheet.

# 10. DESCRIPTION OF STUDY INTERVENTION(S), COMPARATORS AND STUDY PROCEDURES (CLINICAL)

This project is observational only. It is not interventional.

## 10.1. Description of study intervention(s)

Not applicable

## 10.2. Description of comparator(s)

Not applicable

## 10.3. Description of study procedure(s)

Not applicable

## 10.4. Device safety

All devices used to collect clinical data are CE marked medical devices used within the scope for the device registered by its manufacturer. All devices and the procedures have been risk assessed and have been determined to present extremely low risk to the participants.

No NHS affordable smart watches are available with CE medical device approval at this time. Smart watches will not be used to return medical data in this trial but non-medical device watches will be issued to patients who have no history of allergies or dermatitis, to provide trend data to drive the compliance processing. The device used will be a mainstream product built in ISO13485 accredited facilities to medical quality control.

In **Phase 1**, participants will be checked by the Health Research Assistant at each visit for any sign of minor skin reaction; in **Phase 2**, participants will be advised in the initial home visit to report any skin reaction or other problem to the research team. If there are any issues, the device will be taken back from the participant.

## 10.5. Maintenance and storage of devices

L2S2 opens, tests and charges all purchased devices on arrival in a sterile facility in its premises in Cambridge. The devices are then turned off and stored in labelled plastic bags. When devices are to be despatched to participants their charge state is checked again and software is put on the device. The sealed devices are sent by courier to the HRAs (or care homes) who will assign each device to a participant. This is done with the device in the sealed bag which is not opened until the device is first used by the participant.

When the device needs to be taken back, the patient, HRA or care home employed professional will place the device(s) in biological control bags and return them to the Cambridge site either for cleaning, disinfecting or sterilising according to approved procedures set out in ISO13485, or for safe disposal if the device is not to be reused. Devices that can be cleaned in the field like the blood pressure meter are assessed to be low risk and may be cleaned with DiffX wipes or spray. The HRA will use a cleaning protocol wizard on a section of the Reassure OneApp application only visible to research team staff to provide a complete, auditable trail of cleaning / sterilisation procedures.

The HRA will record the condition of the devices at each visit and will clean them / remove them as appropriate to ensure safety is not compromised.

## 10.6. Device ownership

It is made clear to the participants at the start that the devices issued to them are loaned and that they will be collected at the last study visit by the HRA.

## 10.7. Baseline Assessments (Visit 1)

This is an observational study using devices that give accurate measurements. As soon as a participant is measured, the research team's software will start to establish the participant's norms to allow the analytics processing to take into account natural variation. The purpose of the first meeting is (for participants who self-monitor) to train the participant and issue equipment so that the HRA can confirm that the participant knows how to use the devices safely and effectively to collect a first set of data.

Each participant will have a schedule for taking health measurements that will be accessible on their loaned smartphone via the Reassure OneApp application.

## 10.8. Subsequent Visits

In **Phase 1,** visits will be made in the participants' care homes twice-weekly and will take approximately 20 minutes. These will be undertaken either by HRAs from the research team or by care home employed professional, depending on the preference of the care home. They will continue for the 12 week duration of the study.

In **Phase 2**, these visits may also be performed at the participant's request in their own home and will take approximately 20 minutes.

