#### 5.2. Method

The study will use patient data held in care home and GP records to identify potential participants. Health professionals working for the participating care homes or GP surgeries will then use inclusion and exclusion criteria to select patients for invitation to join the study. In the care home phase (Phase 1), the care home manager will sign and hand an invitation letter and Patient Information Leaflet to the potential participants whom they have identified and ask them to sign an attached form giving consent to be approached by the research team for informed consent. In Phase 2, the primary care phase, GP surgery staff will send the invitation letter and Patient Information Leaflet to potential participant and process the returned forms, booking informed consent appointments. The research team is seeking the support of the North Thames Clinical Research Network in parallel with the application to the HRA/REC; if successful, staff from the CRN will support the recruitment and consenting process in Phase 2 only.

The study cohort will be taken from those who have needed most urgent care and who have the largest number of comorbidities, as defined by the inclusion and exclusion criteria above.

**Phase 1** of the study will be conducted with up to 100 participants residing in care homes. Either Health Research Assistants employed by the research team or local care home employed professionals (the choice between these two to be at the care home's discretion) will use connected medical devices to collect data from the cohort at twice-weekly intervals for twelve weeks. In this phase **all devices will be used with all participants**.

NHS activity data will be obtained from the records held in GPs' clinical systems at the end of Phase 1 to enable models to be constructed that will test the study hypothesis and allow the mapping of chronic conditions to device types to be optimised. This will mean that in **Phase 2**, participants will only be asked to use devices that have been proved in **Phase 1** to be effective at collecting useful data relevant to their specific set of co-morbidities.

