#### 7. STUDY DESIGN

The study type will be observational, collecting data from wearables and remote monitoring medical devices to determine correlations with primary data collected from GP surgeries attended by the participants in the course of the study.

Participants will be recruited by West Essex CCG from patients in their region who meet the study inclusion criteria.

The first phase of research with up to 100 participants will be conducted in care homes with twice-weekly visits from Health Research Assistant's (HRA) employed by the research team, equipped with a standard kit of medical devices who will ensure the devices are used appropriately to maintain data quality and who will monitor the effectiveness of the electronic devices. If care homes would rather be trained to undertake these duties using their own staff, the research team will train them and remunerate the care home for these staff costs.

The second phase of 500 participants will be conducted in participants' homes and care homes with visits from a research team HRA to ensure safe and effective use of condition specific wearable and monitoring devices when this is requested. Visit frequency will be automatically adjusted by feedback from the monitoring systems. (Typically once per week.)

The electronic devices will provide primary medical data as well as metadata regarding battery charging behaviour, adherence to study procedures, effect of active compliance management and direct feedback from the participants. The visit frequency will be adjusted to ensure maximum effectiveness of the equipment and to maximise economic benefit to allow a 'best practice' baseline to be established.

The medical devices issued to each patient will be determined by observations and data collected by the HRAs in conjunction with baseline data derived from GP data.

In **Phase 1**, all devices will be used to take measurements from all participants. Devices will be issued to HRAs who will use them to ensure correct use and valid data.

In **Phase 2**, devices will be allocated to participants based on data gathered in **Phase 1**. It is anticipated that this will demonstrate the best combinations of devices for recording health measurements for different sets of co-morbidities, and prove or disprove the following assumptions:

Clinical Research Protocol L2S2 ltd Page 16 of 38

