## 7.1. Visit Plan

## **Phase One**

- 1. Meeting with the participant to explain the purpose and form of the study and gain consent, conducted by a member of the project team. Average meeting time 30 minutes.
- 2. Research team will talk to care home professionals to gain participant's medical history, current medication and urgent care attendance history from locally-held record.
- 3. Initial meeting between the research team Health Research Assistant (HRA) and participant (or care home employed professional and participant). The timetable for the study will be discussed and dates for routine visits will be agreed as far as is possible. The HCA will conduct risk assessments to ensure that the patient can be tested safely. The HCA will use medical devices appropriate to the participant's medical condition determined by the HCA and historical data if available. Average meeting time 30 minutes.
- 4. Follow up visits by the HCA twice weekly to take measurements from the participant using all devices. This is expected to last for approximately 12 weeks per participant, but will end when either the participant exacerbates, elects to drop out of the study or the study ends.

Clinical Research Protocol CONFIDENTIAL

L2S2 ltd Page 17 of 38

5. A final visit will be conducted at the end of the study to ensure patients understand their rights with respect to data processing and retention. Average meeting time 30 minutes.

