## 10.12. Early Discontinuation/Withdrawal of Participants

During the course of the study a participant may choose to withdraw early from the study treatment at any time. This may happen for several reasons, including but not limited to:

- The occurrence of what the participant perceives as an intolerable adverse event
- Inability to comply with study procedures
- Participant decision

Participants may choose to stop the study assessments.

Participants may also withdraw their consent, meaning that they wish to withdraw from the study completely.

 Participants may withdraw from active participation but allow the study team to continue to access their medical records and any relevant hospital data that is recorded as part of routine standard of care.

2) Participants can withdraw from the study but permit data and samples obtained up until the point of withdrawal to be retained for use in the study analysis. No further data would be collected after withdrawal.

In addition, the Investigator may discontinue a participant from the study treatment at any time if the Investigator considers it necessary for any reason including, but not limited to:

- Ineligibility (either arising during the study or retrospectively having been overlooked at screening)
- Significant protocol deviation
- Admission to hospital care
- Clinical decision

Following a complete withdrawal, confirmation will be sent to the participant confirming destruction of all personal data.

All data obtained from registered/enrolled participants will be analysed. Withdrawal from the study may result in exclusion of the data for that participant from certain analyses.

If participants leave the study for any reason a substitute will be sought to maintain study numbers to provide as high a volume of data as possible to train the machine learning.

The type of withdrawal and reason for withdrawal will be recorded in the Case Report Form (CRF).

If the participant is withdrawn due to an adverse event, the Investigator will arrange for follow-up visits or telephone calls until the adverse event has resolved or stabilised.

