#### 12. STATISTICS AND ANALYSIS

## 12.1. Statistical Analysis

Studies to measure interventions are designed using power calculations that minimise the risk of not finding a difference between treatments if one exists (a type II error).

In a purely observational study, such calculations are less relevant, but the study design still needs to provide assurance that sufficient data will be collected to but for this study.

This is mainly achieved by ensuring that the target population has a high event frequency of the index condition — in this case deterioration of healthcare such that hospital admission would be necessary. The mean time of residence for a patient in nursing home care is approximately 15 months, but with half the residents dying in the first six months of residence.

https://www.geripal.org/2010/08/length-of-stay-in-nursing-homes-at-end.html?m=1

Following the protocol described below, a cohort of elderly people (>65 years) living independently and in care/nursing homes, with

- a moderate or high degree of frailty,
- comorbidities as defined in the appendix using standardised NHS list
- a history of regular NHS activity will be identified.

Stage 1 of data collection will feature a universal monitoring plan across for nursing home residents and, following analysis, Stage 2 of data collection will ensure measurements are collected with frequency and using devices appropriate to the needs of different participants by tailoring the frequency and type of monitoring to the needs of the condition and patient.

To provide assurance that the sample size is likely to provide sufficient event frequency, a power calculation was performed (Jones et al. 2003).

Data provided by the West Essex CCG was used to explore different incidence rates of index episodes of health deterioration requiring NHS treatment in the target population as defined above.

As 50% of the nursing home population is likely to die within six months of admission, the recruitment of existing nursing home patients means event prevalence rates of 55% is a conservative estimate.

The lowest acceptable sensitivity of the algorithm was assumed to be 85% (SN) and the lowest acceptable specificity – 80% (SP). A confidence interval of 5% (W) was selected. The required sample size can be determined via the sensitivity or the specificity limit, depending on priorities:

$$N(SN) = \frac{TP + FN}{P} = 1.96^2 * \frac{(SN(1 - SN))}{W^2}$$

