# unique patients												
Stage I		nursing/ indep. care living						# unique patient non- episode		# unique patient episode		
incidence of an episode	month	new	old	new	old	total	dropout	cumulative patients	month	cum	month	cum
35%	1	100				100	7	100	65	65	35	35
35%	2	42	58			100	7	142	65	130	35	70
35%	3	42	58			100	7	184	65	195	35	105

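### The two planning tables in 12.1 print running sums of monthly counts as unique patients, and the text gives 100 for Phase 1 where the Stage I table recruits 184

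*Protocol*

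**What the plan says.** **Length of Phase 1 follow-up.** Section 10.8 says of the twice-weekly visits: "They will continue for the 12 week duration of the study". Section 5.2 has staff "collect data from the cohort at twice-weekly intervals for twelve weeks". Section 7.1, Phase One, step 4 is fuller: "This is expected to last for approximately 12 weeks per participant, but will end when either the participant exacerbates", or on dropout or at study end. Section 10.12 separately lets the investigator discontinue a participant, and one listed reason is "Admission to hospital care".

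**Phase 1 numbers.** Section 7 states: "The first phase of research with up to 100 participants will be conducted in care homes". Section 5.2 also says up to 100, and the synopsis and the conclusion of 12.1 say 100. Section 10.12 adds: "If participants leave the study for any reason a substitute will be sought to maintain study numbers".

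**Planning tables in 12.1.** Both use an episode incidence of 35% a month.
- Stage I holds 100 residents each month, with 42 new in months 2 and 3, and reaches 184 cumulative patients, 195 non-episode and 105 episode.
- Stage II starts with 500, falls to 464 and 430, and reaches 907 non-episode and 488 episode.
- The headings over these counts call them unique patients, for example "unique patient episode".

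**Basis of the sample size.** The lowest acceptable sensitivity is 85%, the lowest acceptable specificity 80%, and W is 5%. Section 12.1 adds: "The required sample size can be determined via the sensitivity or the specificity limit", according to priorities.

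**The concern.** A count of unique patients cannot exceed the number of patients recruited, yet the non-episode totals in both tables do. The sample-size formulas in 12.1 need numbers of separate people with and without an episode. A reader who sets the printed 488 and 907 against those needs sees a wide margin that the tables do not establish.

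The Stage I figures also depend on a rule and a recruitment total that are not stated consistently. Whether visits stop at exacerbation decides whether readings exist after the event, how many residents must be recruited, and whether the 105 episodes belong to 105 different people. A care home working from 10.8 alone would not learn that visits stop at exacerbation. A reader of the synopsis would not expect 184 recruits.

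**Working it through.** **1. Reproduce Stage I.** Inputs from the table: 100 in place, 35 episodes and 7 dropouts a month.
- Carried over: 100 − 35 − 7 = 58, as printed. New each month: 35 + 7 = 42, as printed.
- Cumulative patients: 100 + 42 + 42 = 184, as printed.
- Episodes: 3 × 35 = 105. Non-episodes: 3 × 65 = 195. Both as printed.
- Sum: 105 + 195 = 300 = 3 × 100 patient-months.

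The table therefore applies the 7.1 exit with full replacement. Under that rule the 105 are different people, but the 195 cannot be. Unique non-episode patients number 184 − 105 = 79. As a check, 65 in month 3 plus the 7 + 7 who dropped out in months 1 and 2 gives 79.

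**2. Reproduce Stage II.** Inputs: 500, 464 and 430 present; 36 dropouts in month 1.
- 500 − 36 = 464, so patients with an episode stay in and nobody is replaced.
- Episodes: 175 + 162 + 151 = 488. Non-episodes: 325 + 302 + 280 = 907. Both as printed.
- Sum: 488 + 907 = 1,395, against 500 + 464 + 430 = 1,394 patient-months (rounding).

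The 907 exceeds the 500 enrolled. The 488 counts a patient again for each further month with an episode.

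**3. Stage II in people.** The protocol does not say how far episodes recur in the same people, so a range is needed.

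| Assumption | With episode | Without episode |
|---|---|---|
| Same people every month, no dropout | 500 × 0.35 = 175 | 325 |
| Independent months, no dropout | 500 × (1 − 0.65³) = 363 | 137 |
| Independent months, 7.2% monthly dropout (36/500) | 344 | 156 |

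In the last row the event-free number goes 500, then 500 × 0.65 × 0.928 = 302, then 302 × 0.65 × 0.928 = 182. Episodes are 0.35 × (500 + 302 + 182) = 344. The 156 includes people who dropped out event-free.

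**4. What the stated precision needs.**
- Episode patients: 1.96² × 0.85 × 0.15 / 0.05² = 196.
- Non-episode patients: 1.96² × 0.80 × 0.20 / 0.05² = 246.

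The printed N(SN) at 35% is 560 = 196/0.35, which reproduces. The printed N(SP) at 35% is 301 = 196/0.65, which uses 0.85. At the stated 0.80 it is 246/0.65 = 378.

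**5. Compare.** Specificity half-width is 1.96 × √(0.16/n).

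| Non-episode patients | Half-width (points) |
|---|---|
| 325 | 4.3 |
| 246 | 5.0 |
| 156 | 6.3 |
| 137 | 6.7 |

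Full repetition meets the 246 (325) but misses the 196 (175). Independent months meet the 196 (363) but miss the 246 (137). With 500 people and no dropout, both are met only if between 196 and 500 − 246 = 254 have an episode.

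**The case against.** **The follow-up rules need not conflict.** Section 7.1 gives the 12-week period and its exceptions in one sentence, while 5.2 and 10.8 can be read as the nominal length. Neither mentions dropout, and nobody would take them to forbid it. This largely stands. A reader might infer a flat contradiction, but the documents support only an omission in 10.8 and 5.2.

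**100 and 184 can be reconciled.** The Stage I table prints a total of 100 each month beside the cumulative 184, and 10.12 seeks substitutes. This also largely stands. What remains is that the synopsis, 5.2, 7 and the conclusion of 12.1 give only the 100 and do not say that it means residents under observation at one time.

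**The heading may cover monthly counts.** Each monthly figure is unique within its month, and the cumulative column is a running sum. That explains how the figures arose. It does not make 195 of 184 or 907 of 500 a count of unique patients.

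**12.1 concludes only that enough index events will occur, in an exploratory study.** It promises no specificity precision, allows sizing on either limit, and does not fix whether specificity is counted per person or per reading. This stands against any claim that the study is too small. It does not rescue the tables. If patient-months were the intended unit, the headings are wrong, and repeated months in one person are not the independent observations that the formula assumes.

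**Conclusion.** The labelling fault is certain, because it follows from the printed figures alone. Stage I's 195 and Stage II's 907 cannot be people, and Stage II's 488 is a sum of monthly counts that includes repeat patients. The gap between the 100 in the text and the 184 in the table, and the missing exit rule in 10.8 and 5.2, are real but smaller. Other parts of the protocol largely explain both.

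A reader might go further and infer that Stage II falls short for specificity (about 156 non-episode patients against 246), or conversely that the need for 196 episode patients is safely met. The documents support neither. Both rest on independent months at 35%, which the protocol does not state, and section 5 says it targets people with repeat hospitalisations. Over the range from full repetition to independence, before dropout, Stage II has about 175 to 363 people with an episode and 137 to 325 without. The specificity half-width is about 4.3 to 6.7 points. Each requirement is met only in part of that range, and the printed totals hide this.

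**What to change.** - Rebuild or relabel both tables in 12.1 with one counting unit, and state the replacement assumption of each. If the headings keep unique patients, Stage I becomes 184 recruited, 105 with and 79 without an episode. Stage II becomes a range with its assumption named: 175 to 363 with and 137 to 325 without before dropout, or about 344 and 156 for independent months with 7.2% monthly dropout.
- Restate in 12.1 the precision these counts give. Say that 196 episode patients and 246 non-episode patients (at 80% specificity) are reached only under some assumptions about repeat events.
- In the synopsis, 5.2, 7 and the conclusion of 12.1, say that 100 is the number under observation at once in Phase 1 and that about 184 recruits are expected.
- Add the exit rule of 7.1 to 10.8 and 5.2.

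The cost is protocol wording and the recalculation of two small tables. The stated figures become less favourable, but no enrolment is needed beyond what the Stage I table already plans.
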